- **Procedure related:** pain, tragus site abrasion or bruising

Randomization scheme: Patients will be allocated to LLTS or sham in a 1:1 ratio at time of implant based on random number generator.

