3. SUBJECT SELECTION AND WITHDRAWAL

Sites:

Subjects selected for study will be recruited from the University of Chicago Medical Center (Chicago, IL).

Eligibility:

Eligible patients will be all patients undergoing CABG and/or valve surgery.

Inclusion Criteria:

1. Patients ≥ 18 years of age, <90 years of age
2. Estimated life expectancy of at least 1 year at the time of enrollment
3. History of sinus rhythm or paroxysmal atrial fibrillation

Exclusion Criteria:

1. Patients ≥ 90 years of age, <18 years
2. Patients with known prior history of persistent or permanent AF
3. Atrial Fibrillation occurrence within the last 24 hours of procedure
4. Urgent or Emergency cases
5. Pregnant patients
6. Patients undergoing the following cardiac procedures: heart transplant, pulmonary thromboendarterectomy, isolated aortic arch procedures, congenital heart disease, ventricular assist device insertion, extracorporeal membrane oxygenation insertion, and surgical AF ablation
7. Antiarrhythmics prior to surgery (Class I and Class III)
8. High degree AV block requiring temporary pacing
9. MAZE procedure

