5. STUDY PROCEDURES

Pre-Stimulation:

- Patients will be screened for study
- Discomfort threshold bilaterally will be measured (20 Hz) for 5 minutes
- Pre-implant ECG reviewed (to be performed on day of screening)
- Baseline transthoracic echocardiogram (TTE) reviewed (does *not* need to be performed during inpatient hospitalization; outpatient or outside-hospital TTE report may also be performed)
- NYHA functional class to be determined by treating physician
- Operating physician will be informed of patient randomization allocation to facilitate planning of procedure

Randomization, Implant, and Periprocedure Care:

- LLTS or sham will instituted upon arrival in PACU/recovery after surgery with right sided LLTS. The site of stimulation will alternate every 4 hours between right and left tragus for total stimulation duration of 48 hours.
- Postoperative care for the cardiac surgical patient will be performed as per routine standard of care by the treating primary team
- The patient will be maintained on telemetry during the entire inpatient hospitalization
- Telemetry will be checked daily to evaluate for any new-onset AF
- Predischarge ECG will be performed at the time of hospital discharge
- The patient will be fitted with a 14-day event monitor (i.e. Zio patch or Cardionet monitor) at the time of discharge or to be mailed to the patient/picked-up by patient immediately after discharge on a weekend discharge day
- Blood will be collected for C-reactive protein measurement to assess inflammation per routine lab assessments

Follow-Up Visit (can be performed between 2 weeks and 1 month after discharge):

- The patient will return the 14-day monitor, if not already mailed back
- Routine clinical check as per primary team

Future contact:

- Patients will be asked to participate in an extended registry (protocol IRB16-0272) to evaluate longer-term clinical outcome after study completion. Patients will be asked to sign a separate consent form for participation in this study.

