8. SAFETY AND ADVERSE EVENTS

Safety:

As noted above, periprocedural complications will be logged with respect to procedure, system-related, and lead-related events. All complications will be independently reviewed at the midpoint by the primary investigator (PI). Should there be a trend towards increased complication risk, the study will be halted.

Adverse Events:

As noted above, all adverse events associated with devices will be monitored periprocedurally and continuously through the study. The PI will independently review all events after randomization of 20 subjects in order to make a determination for continuance.

Adverse Effect Documentation:

1. Sinus bradycardia or AVB after stimulation
2. Discomfort or possible skin abrasion due to tragus stimulation
3. Major organ-system failure
4. Death

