15. APPENDIXES

A. FIGURES

Figure 1: Parasymp Device

Figure 2: Electrode attached to tragus

B. J AM COLL CARDIOL 2015;65:867–75

 Low-level
transcutaneous stimu

C. SCHEDULE OF EVENTS (SCHEMA)

	Screening	Surgery (Day 0)	Post-Op Days 1-2	Day of Discharge	Follow-Up Visit (2 weeks to 1 month after discharge)
Medical Records Review	X				X
Clinical Evaluation (Physical Exam, Vital Signs, Medication Review)	X	X	X	X	X
Electrocardiogram	X			X	
Echocardiogram	X ^a				X ^a
Urine Pregnancy Test	X ^b				
NYHA Functional Class Determination	X				
Randomization	X ^c				
LLTS or Sham Application		X ^d	X ^e		
C-Reactive Protein Blood Test		X ^f	X ^f		
Event Monitor (i.e. Zio Patch or Cardionet Monitor)				X ^g	X
Adverse Events		X	X	X	X

^a Results from records review, if available

^b Only for women of childbearing potential

^c Pre-procedure to facilitate planning of procedure

^d Immediately after surgery

^e Continuous for 48 hours

^f If clinically indicated

^g Pre-discharge if discharged on a weekday; arrangement for mailing or pick-up for patients discharged on a weekend day

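### Randomisation time is contradictory, and exclusions 3, 6, 8 and 9 are not tied to a point before it, so exclusion after allocation is left open

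*Combined protocol and SAP*

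**What the plan says.** **When patients are randomised.** The randomisation scheme in Section 2 states: "Patients will be allocated to LLTS or sham in a 1:1 ratio at time of implant based on random number generator". Section 2 has the clip placed at the end of surgery, and Section 5 starts treatment in recovery: "LLTS or sham will instituted upon arrival in PACU/recovery after surgery with right sided LLTS". The Schedule of Events (Appendix C) instead marks randomisation in the Screening column, with footnote c: "Pre-procedure to facilitate planning of procedure". Section 5, under Pre-Stimulation, adds: "Operating physician will be informed of patient randomization allocation to facilitate planning of procedure".

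**Which exclusions are affected (Section 3).**
- Exclusion 3: "Atrial Fibrillation occurrence within the last 24 hours of procedure".
- Exclusion 6 begins "Patients undergoing the following cardiac procedures: heart transplant, pulmonary thromboendarterectomy, isolated aortic arch procedures, congenital heart disease, ventricular assist device insertion" and goes on to extracorporeal membrane oxygenation (ECMO) and surgical AF ablation.
- Exclusion 8: "High degree AV block requiring temporary pacing".
- Exclusion 9 is the MAZE procedure.

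Exclusion 7, on antiarrhythmic drugs, is limited to the time before surgery. Exclusion 8 has no such limit.

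**What happens afterwards.** Section 8 lists "Sinus bradycardia or AVB after stimulation" among the adverse effects to document. Section 6 analyses patients by allocation and says explicitly that those who refuse the ear clip are kept as intention-to-treat. The heading of Section 3 mentions withdrawal, but the section contains no withdrawal rule.

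**The concern.** Eligibility should be settled before the arm is assigned. If the schedule is followed, the arm is assigned first, and the operating physician knows it while some exclusions can still be triggered. A decision to add a listed procedure, or to treat a patient as ineligible, could then depend on the arm. Section 6 has AF timing read by blinded physicians, but that does not protect the question of who is in the comparison.

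Exclusion 8 raises a second problem that remains under either randomisation time. High-degree block that first appears during the 48 hours of stimulation meets the exclusion as worded, and it is also an adverse effect under Section 8. The primary safety endpoint in Section 2 names only pain, abrasion and bruising, so AV block is captured through the Section 8 list alone. With 40 patients per arm and a review after 20 randomised subjects, treating even one or two such patients as ineligible could matter.

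**Working it through.** **1. The two randomisation times.** Section 2 places allocation at device application, which Sections 2 and 5 put after the operation. Appendix C places it at Screening. The Section 5 instruction to tell the operating physician, so that the procedure can be planned, can be followed only if allocation precedes surgery. The documents describe no step before or during surgery that differs by arm: Section 2 measures the discomfort threshold in all participants.

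**2. What each time leaves unsettled.**

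| Exclusion | Allocation at Screening | Allocation at device application |
|---|---|---|
| 3 | Open, unless screening falls just before the procedure | Settled |
| 6 and 9 | Settled for the planned operation; open if the operation changes | Settled for the operation performed |
| 8 | Open for block arising during or after surgery | Open only for block arising after device application |

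**3. Rule for a patient who meets an exclusion after allocation.** There is none. No text removes such a patient. The general sentence in Section 6 assigns patients to their randomised group, and the explicit intention-to-treat sentence covers refusal only.

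**4. The plan's own sample size.** Inputs from Section 6: event rates 0.50 and 0.20, two-sided alpha 0.05, 80% power, unpooled Z-test, 10% dropout.

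n = [0.5×0.5 + 0.2×0.8] × (1.960 + 0.842)² / 0.30² = 35.76, so 36 per arm. Then 36/0.90 = 40 per arm, N = 80. The stated figure is reproduced. Power at 36 per arm is Φ(0.30/√(0.41/36) − 1.960) = 80.3%. Section 6 gives the higher rate to the treatment group, against the hypothesis; swapping the labels changes neither n nor power.

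**5. Power, for assumed removals.** The removal shares are not in the documents. They apply to both arms, on top of the planned 10% dropout.

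| Extra removal | Evaluable per arm | Power | N to keep 36 per arm |
|---|---|---|---|
| 5% | 34.2 | 78.2% | 86 |
| 10% | 32.4 | 76.0% | 90 |
| 15% | 30.6 | 73.6% | 96 |
| 20% | 28.8 | 71.0% | 100 |

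**6. Bias, for assumed removals.** Let b be the event rate in both arms with no true effect, x the share removed from the stimulation arm only, and r the event risk in those removed. The remaining rate is (b − xr)/(1 − x), so the spurious benefit is x(r − b)/(1 − x). Take b = 0.35, the midpoint of the two planned rates:
- x = 0.05, r = 0.75: 0.05 × 0.40/0.95 = 2.1 points.
- x = 0.10, r = 1.00: 0.10 × 0.65/0.90 = 7.2 points.
- x = 0.15, r = 1.00: 0.15 × 0.65/0.85 = 11.5 points.
- r = 0.35, any x: zero.

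Starting instead from an assumed real difference of 50% against 20% (8 events in 40 on stimulation), removing two patients with events gives 6/38 = 15.8% and moves the difference from 30.0 to 34.2 points. That inflates a real effect; it does not create one.

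**The case against.** A reader might infer that patients are definitely randomised at screening, and that four exclusions therefore cannot be settled by then. The documents do not support this. The section that defines randomisation says otherwise, and under it exclusions 3, 6 and 9 are known before allocation. Exclusions 6 and 9 also read naturally as the planned operation, since the eligibility line speaks of patients undergoing surgery in the same way. Urgent and emergency cases are already excluded. The interval from screening to surgery is not stated, so exclusion 3 might be checked close to the procedure. Exclusion 8 stands in a baseline list and can be read as a pre-existing condition.

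A stronger inference would be that the plan removes stimulated patients because of an effect of stimulation and so hides its main cardiac safety signal. The documents do not say this either. No text orders removal. Section 6 states analysis by allocation, and the ear-clip sentence can be read as an example of that rule. Section 8 monitors adverse events throughout, so leaving a patient out of the efficacy analysis need not lose the event. The Section 8 item covers AV block of any degree and exclusion 8 only high-degree block needing pacing, so they overlap without being identical. Nothing indicates that affected patients would be sicker or mostly in the active arm.

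These objections narrow the point. What stands is the contradiction on timing, the operator's knowledge of the arm, the missing time limit in exclusion 8, and the absence of an explicit rule for ineligibility found after allocation.

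**Conclusion.** The point holds as a contradiction with a practical consequence. Section 2 conflicts with Section 5 and Appendix C on when patients are randomised. If the schedule is followed, allocation can precede settled eligibility while the operator knows the arm. Under either time, exclusion 8 read literally reaches block that arises during stimulation. Arm-related exclusion after randomisation is an open risk, not an instruction in the plan.

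Its size cannot be derived from the documents. The ranges of 2.1 to 11.5 points of spurious benefit, and of power falling from 80.3% to between 78.2% and 71.0%, rest entirely on assumed removal shares and, for the bias, on one-sided removal of patients at raised risk. If those removed have average risk, the bias is zero. N = 80 is correct on its own stated inputs. The change is still worth making, because it alters conduct at little cost and closes most of the risk.

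**What to change.** - **Randomisation time.** Reconcile Sections 2 and 5 and Appendix C on the Section 2 timing: draw the allocation once surgery is complete, immediately before the device is applied. Move the Appendix C entry out of the Screening column, correct footnote c, and delete the Section 5 bullet that informs the operating physician.
- **Section 3.** State that every exclusion, including 3, 6, 8 and 9, is assessed before the allocation is drawn and that none is applied afterwards.
- **Section 6.** State that every randomised patient stays in the allocated group for the intention-to-treat analysis, whatever is found later about eligibility.
- **Section 8.** State that AV block after device activation is recorded as an adverse effect and is not a ground for exclusion from the analysis.

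These changes concern eligibility and analysis only, not how AV block is managed.

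**Cost.** Someone must make the draw at the end of surgery. Some consented patients will not be randomised, so more than 80 consents will be needed; the documents do not allow the number to be estimated. No extra assessment is required, and the target of 80 randomised patients does not change.

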4. STUDY DEVICE

LLTS will be performed using a transcutaneous electrical nerve stimulation (TENS) device (Parasym, Parasym Health). This device consists of a battery-powered, programmable TENS unit and a pair of stimulation electrodes that can be clipped to the tragus of the external ear in order to stimulate the auricular branch of the vagus nerve (see Appendix A, Figures 1-2). There is no known interaction with other cardiac devices (e.g., pacemakers and defibrillators)

The device was cleared by the FDA as a Class II device based on Section 882.5890 (see <https://www.accessdata.fda.gov/scripts/cdrh/cfdocs/cfrl/ldetails.cfm?lid=157705>). This is a non-significant risk device. It has not been subject to any advisories or recalls.

5. STUDY PROCEDURES

Pre-Stimulation:

- Patients will be screened for study
- Discomfort threshold bilaterally will be measured (20 Hz) for 5 minutes
- Pre-implant ECG reviewed (to be performed on day of screening)
- Baseline transthoracic echocardiogram (TTE) reviewed (does *not* need to be performed during inpatient hospitalization; outpatient or outside-hospital TTE report may also be performed)
- NYHA functional class to be determined by treating physician
- Operating physician will be informed of patient randomization allocation to facilitate planning of procedure

Randomization, Implant, and Periprocedure Care:

- LLTS or sham will instituted upon arrival in PACU/recovery after surgery with right sided LLTS. The site of stimulation will alternate every 4 hours between right and left tragus for total stimulation duration of 48 hours.
- Postoperative care for the cardiac surgical patient will be performed as per routine standard of care by the treating primary team
- The patient will be maintained on telemetry during the entire inpatient hospitalization
- Telemetry will be checked daily to evaluate for any new-onset AF
- Predischarge ECG will be performed at the time of hospital discharge
- The patient will be fitted with a 14-day event monitor (i.e. Zio patch or Cardionet monitor) at the time of discharge or to be mailed to the patient/picked-up by patient immediately after discharge on a weekend discharge day
- Blood will be collected for C-reactive protein measurement to assess inflammation per routine lab assessments

Follow-Up Visit (can be performed between 2 weeks and 1 month after discharge):

- The patient will return the 14-day monitor, if not already mailed back
- Routine clinical check as per primary team

Future contact:

- Patients will be asked to participate in an extended registry (protocol IRB16-0272) to evaluate longer-term clinical outcome after study completion. Patients will be asked to sign a separate consent form for participation in this study.

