REFERENCE THERAPY	The reference therapy will be a sham control group; i.e., patients on whom an LLTS device with a non-functioning electrode will be applied and in whom therapy will not be delivered.
STATISTICAL METHODOLOGY	Traditional statistical methods will be employed. The student's T-test will be used for continuous comparisons. Fisher's exact or the Chi-square test will be applied for dichotomous variables. Time to endpoint analysis will be performed using the Kaplan-Meier method.

LIST OF ABBREVIATIONS

AAD	ANTIARRHYTHMIC DRUG THERAPY
ACE-I	ANGIOTENSIN-CONVERTING ENZYME INHIBITOR
AF	ATRIAL FIBRILLATION
ARB	ANGIOTENSIN RECEPTOR BLOCKER
BB	BETA-BLOCKER
CABG	CORONARY ARTERY BYPASS GRAFT
CRT	CARDIAC RESYNCHRONIZATION THERAPY
FDA	FOOD AND DRUG ADMINISTRATION
GDMT	GOAL-DIRECTED MEDICAL THERAPY
HF	HEART FAILURE
ICD	IMPLANTABLE CARDIOVERTER-DEFIBRILLATOR
IRB	INSTITUTIONAL REVIEW BOARD
LBBB	LEFT BUNDLE-BRANCH BLOCK
LV	LEFT VENTRICULAR
LLTS	LOW-LEVEL TRAGUS STIMULATION
LVEF	LEFT VENTRICULAR EJECTION FRACTION
NYHA	NEW YORK HEART ASSOCIATION
POAF	POSTOPERATIVE ATRIAL FIBRILLATION
POD	POSTOPERATIVE DAY
RA	RIGHT ATRIUM
RV	RIGHT VENTRICLE
SR	SINUS RHYTHM
TTE	TRANSTHORACIC ECHOCARDIOGRAM
UCMC	UNIVERSITY OF CHICAGO MEDICAL CENTER
UofC	UNIVERSITY OF CHICAGO
VT	VENTRICULAR TACHYCARDIA
VF	VENTRICULAR FIBRILLATION

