2. STUDY DESIGN

Study design: Single-blind study. Patients will be randomized, to LLTS versus sham procedure, and remain blinded to their treatment allocation. Both treatment options will utilize similar equipment, namely the use of alligator clips which will be placed on the tragus and earlobe of the right ear for patients (see Appendix A, Figure 2). The distinction is only that in patients assigned to LLTS, they will be initiated on therapy at the time of device placement.

Prior to cardiac surgery, the discomfort threshold of both left and right tragus stimulation will be determined for all participating patients. Intermittent electrode signals, or microcurrents, are delivered at 20 Hz with 200 μ sec pulse width with variable microampere (mA) output. The discomfort threshold is defined as the stimulation intensity in mA at which point patients experience discomfort. The stimulation intensity used in the study will be set just below the discomfort threshold, as established from prior work.¹⁵ The clip will then be placed on the patient's ear at the end of surgery. After surgery is completed, the clip will then be removed and replaced on the contralateral ear. Stimulation will then continue, one ear alternating with the other, every 4 hours for a total of 48 hours. It is possible that the threshold can change during the post-operative period. If the patient shows any sign of discomfort from stimulation, the intensity of stimulation will be reduced to a level at which signs of discomfort disappears.

Follow-up will be performed with 14-day event monitor (i.e. Zio patch or CardioNet event monitor) at the time of discharge.

Electrocardiography (i.e. ECG) will be performed pre-procedure and prior to hospital discharge. Echocardiography will be assessed prior to study initiation and when clinically available in follow-up.

Duration of study: 1 month

Primary endpoints: A combination of clinical and electrocardiographic endpoints will be prospectively studied. These include:

- **Clinical:** Primary clinical endpoint is time to inpatient AF (length of stay >5 days). Secondary endpoint is any occurrence of AF during 14 day post procedure monitoring.
- **Electrocardiographic:** Arrhythmia occurrence (i.e., AF, nonsustained VT, VT or VF requiring device therapy) will be documented throughout the study period

Primary safety endpoint: Procedure-related complications will be assessed prospectively both acutely and throughout the study period, including:

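### Allocation timing conflicts between Section 2 and Section 5 with Appendix C, and the operating physician learns the arm, apparently before surgery, although no described surgical step needs it and two clinician-dependent outcomes are unprotected

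*Combined protocol and SAP*

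**What the plan says.** Three places deal with when allocation happens or who learns it.

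- Section 2, Randomization scheme: "Patients will be allocated to LLTS or sham in a 1:1 ratio at time of implant based on random number generator".
- Section 5, Pre-Stimulation list: "Operating physician will be informed of patient randomization allocation to facilitate planning of procedure".
- Appendix C, Schedule of Events: the Randomization row is marked in the Screening column, with footnote c, "Pre-procedure to facilitate planning of procedure".

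On the device, the Study Summary says that sham patients are those on whom "an LLTS device with a non-functioning electrode will be applied". Section 2 describes similar equipment in both arms and adds: "The distinction is only that in patients assigned to LLTS, they will be initiated on therapy at the time of device placement". It places the clip on the patient's "ear at the end of surgery"; Section 5 starts LLTS or sham on arrival in recovery.

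On blinding, the trial is declared single-blind: patients are randomized "to LLTS versus sham procedure, and remain blinded to their treatment allocation". Section 6 states blinded assessment once, for time to AF. It states none for stay over 5 days, which is the second listed primary outcome and half of the composite used for sample size, and none for Actionable AF, a secondary outcome. Section 5 gives postoperative care to the treating primary team and does not describe its membership or whether it knows the arm.

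**The concern.** A coordinator cannot tell from the plan whether to randomize at screening or at device placement. If the earlier time is followed, a physician involved in the operation knows the arm before any part of the trial needs that knowledge. Two things are then at stake.

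- **Decisions that are outcomes.** Stay over 5 days turns on when a patient is discharged. Actionable AF consists of treatment choices. If the operating physician takes part in or informs those decisions, a difference between arms could arise for reasons other than stimulation. Blinded reading of rhythm recordings does not protect a discharge decision.
- **Exclusions applied after allocation.** Some exclusions in Section 3 can settle late, for example AF in the 24 hours before the procedure. With allocation at screening, they could be applied by someone who knows the arm. The intention-to-treat sentence in Section 6 speaks only of patients who refuse to go on with treatment, so it does not cover this case.

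**Working it through.** **The plan's own figure.** Inputs from Section 6: event rates 0.50 and 0.20, two-sided Z-test with unpooled variance, alpha 0.05, power 80%, dropout 10%.

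n per arm = (1.960 + 0.842)² × (0.50×0.50 + 0.20×0.80) / 0.30² = 7.849 × 0.41 / 0.09 = 35.76, so 36. Then 36 / 0.90 = 40 per arm, 80 in total. The stated size reproduces, and nothing below alters it.

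**When is allocation made, and who learns it?**

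| Place | Timing | Who learns the arm |
|---|---|---|
| Section 2, Randomization scheme | At implant (term not defined) | Not stated |
| Section 5, Pre-Stimulation | Among screening, threshold testing, ECG review and NYHA class | Operating physician |
| Section 5, next list | Its heading names randomization; its first item starts the device in recovery | Not stated |
| Appendix C, footnote c | Screening, before the procedure | Not stated |

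The Schedule alone fixes a preoperative time but names no recipient. Section 5 names a recipient but gives no clock time. The two share the same stated purpose, so together they imply disclosure before surgery.

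**Does any step before or during surgery need the arm?**

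1. The discomfort threshold is measured before surgery in all participants (Section 2), so it does not depend on the arm.
2. The clip goes on at the end of surgery (Section 2), or the device starts in recovery (Section 5).
3. The arms differ only in whether therapy is delivered once the device is on. The non-functioning sham electrode means that whoever applies the device may need the arm, but only then.
4. No described surgical step differs by arm.

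**Could the size be computed?** Not from the documents: they give no discharge practice, no separate rate for stay over 5 days, and no account of who decides. As an illustration only, assume no true effect, 36 evaluable per arm, and a composite rate moved in one arm by s = 5, 10 or 15 points (1.8, 3.6 or 5.4 patients of 36). With SE = √{[p(1−p) + q(1−q)]/36}, the chance of p<0.05 is Φ(s/SE − 1.96) + Φ(−s/SE − 1.96). Example: p = 0.50, q = 0.40 gives SE = √(0.49/36) = 0.1167 and s/SE = 0.857, hence 0.135 + 0.002 = 14%. Fisher's test was enumerated in full.

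| Assumed rates | Test | No shift | 5 | 10 | 15 |
|---|---|---|---|---|---|
| 50%, one arm lower | Z | 5% | 7% | 14% | 26% |
| 50%, one arm lower | Fisher | 2.5% | 4% | 8% | 17% |
| 20%, one arm higher | Z | 5% | 8% | 17% | 30% |
| 20%, one arm higher | Fisher | 3% | 5% | 11% | 22% |

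The shifts are assumptions. The table shows what a shift would do, not that one would occur. By Fisher's test a 5-point shift stays below the nominal 5% in both settings (3.8% and 4.6% before rounding).

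**The case against.** The strongest reply is that the trial is openly single-blind, that clinicians may therefore know the arm, and that the rhythm outcome is read blind. That stands. A reader might infer that telling the operator contradicts the blinding statement, or that it undermines time to AF. The documents support neither: only patients are said to be blinded, and Section 6 has blinded physicians assess time to AF.

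A reader might also infer that the plan expressly discloses the arm before surgery, and without any reason. Neither is supported. The Section 5 heading refers to stimulation, which begins after surgery, so the preoperative timing is an inference made with the Schedule. A purpose is printed; what is missing is any described step that it would serve. The word procedure is also ambiguous. Section 3 uses it for the operation, but Section 2 uses it for the sham intervention and, under procedure-related safety events, for "pain, tragus site abrasion or bruising". The bullet may have meant planning of device placement. Likewise, if implant meant the operation, the timing conflict would narrow, although the Screening column would still differ.

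It can further be said that stay over 5 days is counted from dates, so a blinded assessor would add little. That is right, and it is why the protection must come from what the deciding clinicians know. Finally, bedside staff may learn the arm anyway, since the ear is switched every 4 hours and intensity is lowered on discomfort. That limits what the change can achieve; it does not supply a reason for the early disclosure.

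**Conclusion.** The timing conflict is on the page and must be resolved. On the natural joint reading of Section 5 and the Schedule, the operating physician learns the arm earlier than any described step requires, while a listed primary outcome and a secondary outcome that depend on clinicians' decisions have no stated protection.

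The risk of bias is conditional. It depends on the operating physician taking part in or informing discharge or AF treatment, or on exclusions being settled after allocation; the documents are silent on both. A reader might conclude that stay over 5 days or Actionable AF will be biased, or take the illustrative rejection rates as an estimate. The documents support neither. They do not allow the size to be derived, nor the part due to this disclosure to be separated from single-blind care in general. The point should be fixed because the exposure is avoidable and the change is cheap, not because harm has been shown.

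**What to change.** 1. Delete the disclosure bullet in Section 5. If the procedure it refers to was meant to be device placement, say so and limit disclosure to the person placing the device, at that time.
2. Generate and reveal the allocation at device placement, after exclusions are checked, and only to the role that applies and operates the device. Name that role, including who switches ears and adjusts intensity.
3. Align the Randomization row and footnote c of the Schedule with this.
4. State that those deciding discharge or AF treatment, and the operating physician, are not routinely told the arm, with unblinding allowed for patient safety.
5. Separately, reconcile Sections 2 and 5 on whether the clip is placed at the end of surgery or on arrival in recovery. No view is taken on which is right.

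Items 1 and 3 are wording. The practical cost is that the assignment and the matching electrode must be obtained at the end of surgery or in recovery. Some bedside staff may still learn the arm, so the risk is reduced, not removed. Sample size, alpha and power are unaffected.
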